2.3 Sample size

Considering an incidence of the primary composite end-point in the range of 50% in the Watchman/FLX group, which is a conservative estimate based on previous reports, we estimate that 200 patients will provide greater than 80% power to prove superiority of Amulet as compared to Watchman/FLX assuming a 40% risk reduction (i.e. corresponding to an event rate in the range of 30%) and a significance level of 5% (alpha).

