Study Product / Intervention:	
The WATCHMAN (Atritech, Boston Scientific, Natick, MA, USA) LAAC technology consists of the Access System (Access Sheath and Dilator) and Delivery System (Delivery Catheter and WATCHMAN Device). The Access System and Delivery System permit Device placement in the left atrial appendage (LAA) via femoral venous access and inter-atrial septum crossing into the left atrium. WATCHMAN device is a self-expanding nitinol structure with a porous covering on the proximal face. The device is constrained within the Delivery System until deployment in the LAA. The Device is available in 5 sizes from 21 to 33 mm. The new generation Watchman FLX has a shorter device length and a less taper angle to simplify implantation and to fit a wider range of patients. Furthermore, the frame of the new device is designed to enhance sealing within the left atrial appendage.
 
The AMPLATZER Amulet (St. Jude Medical-Abbott) is a self-expanding device made of nitinol that has a distal lobe and a proximal disc, connected by an articulated waist. The device lobe has six to 10 pairs of stabilising wires and is meant to be implanted in the proximal 10-15 mm of the left atrial appendage (LAA), whereas the device disc is intended to cover the ostium at the left atrial side. The proximal female screw is recessed to minimise thrombus formation on the disc and potentially facilitate re-attachment of the device to the pusher screw. The lobe sizes range from 16 to 34 mm.

Number of Participants with Rationale:	
Total number of patients with primary endpoint assessment: 200 100 patients in the Watchman/FLX group 100 patients in the Amplatzer Amulet group Sample size is calculated to state superiority of Amplatzer Amulet compared with Watchman/FLX

Study Duration:	8 years
Study Schedule:	February 2018 February 2026

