Statistical Considerations:	Assuming an incidence of the primary composite end-point in the range of 50% in the Watchman/FLX group, which is a conservative estimate based on previous reports, 200 patients will provide greater than 80% power to prove superiority of Amulet as compared to Watchman/FLX assuming a 40% risk reduction (i.e. corresponding to an event rate in the range of 30%) and a significance level of 5% (alpha). Primary and secondary end points will be analysed on an intention-to-treat basis. Additional analyses of the primary endpoint will be also carried out in the per-protocol and as-treated populations. Similarly, LAA patency and DRT at 45-day and 13-month CCTA and at 45-day TEE as well as clinical outcomes will also be analyzed in the per-protocol and as-treated population. Categorical outcome measures will be compared using a χ^2 test or Fisher exact test as required. Continuous variables will be compared using a 2-sided unpaired t test or a Mann-Whitney test, as appropriate. Estimation of the cumulative incidence of safety and efficacy endpoints will be performed using the Kaplan-Meier method, and event rates will be compared by the log rank test. The estimated relative risk (RR) is the ratio of the risk probabilities, and a confidence interval will be constructed based on a logarithmic transformation. Correlations between variables will be analysed with a Cox regression.
GCP Statement:	This study will be conducted in compliance with the protocol, the current version of the Declaration of Helsinki, the ICH-GCP or ISO EN 14155 (as far as applicable) as well as all national legal and regulatory requirements.

ABBREVIATIONS

AF	Atrial fibrillation
ACP	Amplazer Cardiac Plug
ACT	Activated clotting time
AE	Adverse Event
AESI	Adverse Event of Special Interest
ASA	Acetylsalicylic acid
BARC	Bleeding Academic research Consortium
CA	Competent Authority (e.g. Swiss medic)
CCTA	Cardiac computed tomography angiography
CEC	Clinical Events Committee
CTU	Clinical Trials Unit
CV	Cardiovascular
DAPT	Dual antiplatelet therapy
DRT	Device related Thrombosis
EC	Ethics Committee
ECG	Electrocardiogram
eCRF	Electronic Case Report Form
EMA	European Medicines Agency
FDA	Food and Drug Administration
GCP	Good Clinical Practice
H1	Alternative hypothesis
HBR	High bleeding risk
Ho	Null hypothesis
ICE	Intracardiac echocardiography
ISO	International Organisation for Standardisation
LAA	Left atrial appendage
LAAC	Left atrial appendage closure

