12.5 Handling of missing data and drop-outs

Patients with missing data for the primary end-point will be excluded from the primary analysis.

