4.1 Confidence intervals and *P* values

Primary and secondary end points will be analysed on an intention-to-treat basis. Additional analyses will be also carried out in the per-protocol and as-treated populations. Categorical outcome measures will be compared using a χ^2 test or Fisher exact test as required. Continuous variables will be compared using a 2-sided unpaired t test or a Mann-Whitney test, as appropriate. Estimation of the cumulative incidence of safety and efficacy end-points will be performed using the Kaplan-Meier method in case of time-to-event endpoints, and event rates will be compared by the log rank test. The estimated relative risk (RR) is the ratio of the risk probabilities, and a confidence interval will be constructed based on a logarithmic transformation.

The primary endpoint LAA patency or adjudicated cross-over including failed cross-over to other device at 45 days will be analyzed using risk ratios and risk differences.

All statistical tests will be performed using a 5% significance level.

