Data expressed as n (%), p-value from Fisher's tests

¶ Justified crossover is defined as the switch from the randomized device to the other device based on morphological/anatomical considerations during device implantation as centrally assessed by an independent and multidisciplinary clinical event committee (CEC). This parameter was included in the composite primary outcome together with *LAA Patency.

CCTA: cardiac computer tomography angiography. TTE: Transthoracic Echocardiography.

CTU Bern	Swiss APERO SAP	Version: 2.0	
	Template: CS_STA_TEM-11	Valid from: 17.08.2021	

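### The stated power above 80% holds for 200 evaluable patients under the uncorrected chi-square test, but not under the Fisher test footnoted for the primary-outcome table

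*Combined protocol and SAP*

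**What the plan says.** **Power.** SAP 2.3 and protocol 12.2 state: "we estimate that 200 patients will provide greater than 80% power to prove superiority of Amulet as compared to Watchman/FLX". The synopsis, under Statistical Considerations, has: "200 patients will provide greater than 80% power to prove superiority of Amulet as compared to Watchman/FLX assuming a 40% risk reduction". All three assume 50% events with Watchman/FLX and a 40% relative reduction, which gives 30% with Amulet. Allocation is 1:1.

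**Who the 200 are.** The synopsis entry on the number of participants reads "Total number of patients with primary endpoint assessment: 200", with 100 per group. The three power statements do not repeat that qualifier. No section gives a number to randomise or an expected rate of missing endpoints.

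**Missing endpoints.** Protocol 12.5: "Patients with missing data for the primary end-point will be excluded from the primary analysis". Protocol 12.4 limits the main analysis to randomised patients who completed 45-day follow-up. The SAP does not repeat the exclusion. Its full analysis set is all randomised patients (4.2.1), and multiple imputation is available only on request (6.2.3, 6.4).

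**The test.** Protocol 12.4 and SAP 4.1 allow a chi-square or a Fisher test for categorical outcomes, as the case requires. SAP 4.1 adds that the primary endpoint is analysed with risk ratios and risk differences, and sets the level: "All statistical tests will be performed using a 5% significance level". SAP 5.7, Table 4, puts the primary composite in its first row with a p-value column, and the footnote reads "p-value from Fisher's tests".

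**The concern.** A power figure belongs to a particular test and a particular number of analysed patients. Here the sample size sections name no test, and they leave open whether 200 is the number randomised or the number analysed. Fisher's test is conservative at this sample size, and the margin above 80% is small, so either choice can move the design across the threshold that it claims to exceed.

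What is at stake is how the result is read. A non-significant primary comparison would be judged against a stated power above 80%. If the p-value comes from Fisher's test, or if 200 turns out to be the number randomised and a moderate share of CCTAs cannot be assessed, the planned power was lower than that.

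**Working it through.** **Inputs.** p1 = 0.50 and p2 = 0.30 (SAP 2.3); alpha = 0.05 (SAP 2.3 and 4.1); n = 100 per arm (synopsis). The sidedness of the primary test is not stated, so two-sided is assumed.

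**Step 1: the plan's figure, normal approximation.**

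Power = Φ{ [√n · |p1 − p2| − 1.960 · √(2p̄(1 − p̄))] / √(p1(1 − p1) + p2(1 − p2)) }, with p̄ = 0.40.

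√(2 × 0.40 × 0.60) = 0.6928; √(0.25 + 0.21) = 0.6782.

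Power = Φ[(10 × 0.20 − 1.960 × 0.6928) / 0.6782] = Φ(0.642 / 0.6782) = Φ(0.947) = 82.8%.

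The claim of more than 80% reproduces. A one-sided 5% test would give 89.8% by the same approximation.

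**Step 2: evaluable patients needed for 80%.**

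n = (1.960 × 0.6928 + 0.842 × 0.6782)² / 0.20² = (1.358 + 0.571)² / 0.04 = 93 per arm, or 186 in all. The slack is 200 − 186 = 14 patients, which is 14/200 = 7%.

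**Step 3: exact power by test.** For each pair (x, y) of event counts, multiply the two binomial probabilities, and sum over the pairs for which the test gives p ≤ 0.05. At 100 evaluable per arm:

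- uncorrected chi-square: 83.2%
- continuity-corrected chi-square: 79.2%
- Fisher's exact test: 79.2%

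Fisher gives 79.9% at 101 per arm and 80.6% at 102 per arm, so it needs 204 evaluable patients to exceed 80%.

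**Step 4: 200 read as randomised, missing endpoints excluded.** The documents give no missing rate. The rates below are assumptions, taken as equal in both arms.

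| Missing (assumed) | Analysed per arm | Chi-square, approx. | Chi-square, exact | Fisher, exact |
|---|---|---|---|---|
| 0% | 100 | 82.8% | 83.2% | 79.2% |
| 5% | 95 | 80.8% | 80.6% | 76.0% |
| 7% | 93 | 80.0% | 79.9% | 75.1% |
| 10% | 90 | 78.7% | 79.3% | 74.9% |
| 15% | 85 | 76.3% | 76.6% | 71.5% |
| 20% | 80 | 73.7% | 73.1% | 67.7% |

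Exact power does not fall smoothly, because the counts are discrete. With chi-square, the crossing below 80% lies at about 5–7% missing.

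**Step 5: 200 read as evaluable.** Missing endpoints then raise the number to randomise and leave the power unchanged. At an assumed 10%, 200 / 0.90 = 222.2, so 223 would be randomised.

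**The case against.** The strongest reply is that nothing is miscalculated. The only place that says what the 200 are makes them patients with the endpoint assessed, and no section says 200 randomised. On that reading, patients excluded under 12.5 are simply not part of the 200. With chi-square the figure then stands in full, at 83.2%. A reader might infer that the power claim is an arithmetic error, or that any missing CCTA defeats it. The documents support neither: the figure reproduces from its own inputs, and even if 200 were the number randomised, chi-square power is still 80.6% at 5% missing.

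Some provisions also limit the loss. Crossover patients count as events in all analyses (SAP 4.2), so they need no CCTA. Protocol 9.1.4 permits imaging outside the window in a pandemic or similar situation, and SAP 6.2.3 examines the effect of delayed scans. These points stand.

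On the test, the general rule permits chi-square. With about 40% events overall and 100 per arm, the expected counts are near 40 and 60, so nothing requires Fisher. The Table 4 footnote may be a blanket note for a table made up mostly of rarer clinical events. That is a fair account of how the footnote arose, but it does not remove the conflict. The footnote covers the row holding the primary composite, it is the most specific statement about that p-value, and SAP 4.1 and 6.2.1 name no other test for that endpoint.

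**Conclusion.** The claim of more than 80% power is correct for 200 patients with an assessable primary endpoint and the uncorrected chi-square test (83.2% exact). It is not met with the Fisher test footnoted for the primary-outcome table: 79.2% at 100 evaluable per arm, 0.8 points below the 80% mark and 4.0 points below chi-square. That shortfall needs no assumption about missing data.

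The missing-data part is conditional. It applies only if 200 means randomised, a reading that the unqualified power statements leave open and the synopsis entry on participant numbers contradicts. Chi-square power then falls below 80% beyond about 5–7% missing; at an assumed 10% it is 79.3%, or 74.9% with Fisher.

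These figures assume a two-sided 5% test, the planned rates of 50% and 30%, equal arms and, for the conditional part, equal missingness in both arms. The shortfall is small and the correction is one of wording. It is worth making because the figure is the trial's only statement of what it was sized to detect.

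**What to change.** 1. In protocol 12.2, SAP 2.3 and the synopsis power statement, say that 200 means patients with an assessable primary endpoint, 100 per arm, as the synopsis entry on participant numbers does.
2. Name one two-sided test for the primary endpoint in SAP 6.2.1 and make the Table 4 footnote agree. Either choose the uncorrected chi-square test and keep the claim of more than 80% (Fisher can stay for the sparse clinical-event rows), or choose Fisher's test and restate the power as about 79%.
3. If fewer than 200 turn out to be evaluable, report the power for the number analysed, at the planned 50% and 30% rather than at the observed rates.

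The test should be settled before the primary comparison is seen by arm. The cost is wording only: no change to data collection or procedures. Under the Fisher option, the stated power becomes slightly less favourable.

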2.4 Framework

We formulate the following hypotheses:

- *Null hypothesis A (HOA): Amulet is superior to WATCHMAN/FLX device in terms of complete LAA occlusion degree and feasibility.*
- *Null hypothesis B (HOB): there is no difference between Amulet and WATCHMAN/FLX in terms of LAA occlusion degree and feasibility.*

2.5 Statistical interim analyses and stopping guidance

No statistical interim analyses are planned.

2.6 Timing of final analysis

The primary endpoint analyses will be performed after all 45 days follow-up visits are conducted and completely entered into the data capture system; and after all data are cleaned and events have been adjudicated. Longer follow-up analyses at e.g. 13 months, 2 years, 3 years, 4 years and 5 years will be conducted as requested, after all data have completely entered into the data capture system; and after all data are cleaned and events have been adjudicated.

2.7 Timing of outcome assessments

Assessment of primary outcome

The primary outcome is the composite of LAA patency at 45 day evaluated with CCTA; or the crossover from one device to the other device based on morphological/anatomical considerations during device implantation, including failed implantation attempts.

Patency LAA will be estimated at CCTA by measurement of the linear attenuation coefficient (Hounsfield unit, HU) in the LAA distal to the device and comparison of contrast density to atrial chamber. LAA patency was defined with LAA HU \geq 100 or LAA HU \geq 25% of LA HU, as reported in a previous publication Saw et al. 2015. Adjunctive CCTA criteria of complete occlusion will be collected in order to validate them.

A TEE evaluation of PDL presence will be performed at 45-days in order to compare the two imaging technique.

Assessment of secondary outcomes

Secondary outcomes will be collected at 45 days, 6 months, 13 months, 2 years, 3 years, 4 years and 5 years follow up. Data about event will be collected both in electronic form that with related document (medical reports, CT and other imaging report). LAA patency on arterial phase has been already defined in the previous section

CTU Bern	Swiss APERO SAP	Version: 2.0	
	Template: CS_STA_TEM-11	Valid from: 17.08.2021	

("Assessment of primary outcome"). LAA patency on venous phase is defined, as reported in a previous publication²², as a LAA density ≥ 100 HU or $\geq 150\%$ of that measured at the same site on arterial phase.

Assessment of safety outcomes

Safety outcomes will be assessed 45 days, 6 months, 13 months, 2 years, 3 years, 4 years and 5 years follow up. Data about adverse clinical events will be collected both in electronic form (ICE-Advice Pharma) that with related document (medical reports, CT and other imaging report).

Assessments in participants who prematurely stop the study

Data of withdrawn participants will be collected up to the time of withdrawn. However, withdrawn participants will be asked the permission to continue collecting and evaluate data about them from routine data or other sources (general practitioners, Health System Softwares available) in order to respect the patient choice without affecting the scientific quality of the study.

CTU Bern	Swiss APERO SAP	Version: 2.0	
	Template: CS_STA_TEM-11	Valid from: 17.08.2021	

Study Periods	Enrolment	Procedure	Post procedural Hospital discharge	45- day follow up	6- month follow up	13- month follow up	2- year follow up	3- year follow up	4-year follow up	5-year follow up
Time point	1	2	3	4	5	6	7	8	9	10
Time	-90 / 0 d	0 d	up to 48 h	45±7 d	180±7 d	395 ±30 d	730±30 d	1095 ±30 d	1460 ±30 d	1825 ±30 d
Type of follow up ¹				Medical contact	Medical contact or phone ²					
Patient Information and Informed Consent	x									
Demographics	x									
Medical History	x			x		x	x	x	x	x
In- /Exclusion Criteria	x									
Physical Examination	x		x	x		(x)	(x)	(x)	(x)	(x)
Vital Signs	x		x	x		x	x	x	x	x
Laboratory test ²	x		x							
Randomization	x ⁵									
12 lead ECG	x	x	x	x		(x)	(x)	(x)	(x)	(x)
TEE	x ³	x ⁴		x ⁴	x ³	(x) ³				
CCTA	x ⁴			x ⁵		(x) ⁵				
Concomitant therapy, Intervention	x		x	x	x	x	x	x	x	x
LAAC		x								
AE ⁶ and SAE collection		x	x	x	x	x	x	x	x	x

¹All types of follow up will be described in Section 9.1.

²In case of impossibility of a follow up by medical contact a telephone contact should be performed. It will consist of reporting vital status, adverse clinical events (as defined in 9.1.8 and Appendix 1) and pharmacotherapy.

³Performed if clinically indicated

⁴As per standard of care

⁵Study specific intervention

⁶As defined in 9.1.8 and Appendix 1

CTU Bern	Swiss APERO SAP	Version: 2.0
	Template: CS_STA_TEM-11	Valid from: 17.08.2021

2.8 Blinding

Allocation to the two randomized devices Amulet vs Watchman/FLX is concealed. After the randomization result is available, the study personnel, monitors, the trial statistician receiving the raw data download are not blinded to the randomized device.

However, independent blinded analyses will be conducted by a second statistician who does not know the allocation result of the randomization (e.g. coded X vs Y). Moreover, also the clinical event adjudication committee adjudicating the events is blinded to the randomized device.

The Sponsor will be provided with blinded tables of the primary outcome analyses (e.g. coded X vs Y with no denominators), which the Sponsor can use for final plausibility checks and queries for e.g. outliers to be send to the centres. If this final cleaning process is performed, the Sponsor will receive the unblinded results.

CTU Bern	Swiss APERO SAP	Version: 2.0	
	Template: CS_STA_TEM-11	Valid from: 17.08.2021	

3. Data management

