8.4 Crossover

In case of impossibility during the procedure to implant the randomized device, operator can choose to implant another device or stop the procedure. In any case the patient will continue to be considered enrolled in the trial. The crossover endpoint will be centrally adjudicated by the Clinical Events Committee (CEC) as justified if there will be evidence that the randomly allocated device has been positioned at least once in the LAA but LAA ostium sealing remained suboptimal (peri-device leak ≥ 3 mm) or concerns were present over the device stability and consequent risk of device embolization.

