9.1.2 Randomization and Procedure

Patients who have signed the informed consent form and meeting all inclusion and exclusion criteria will be included in the study and randomized before LAAC procedure.

After randomization, patients will receive the LAAC with the randomized device. In the event that the patient is randomized to the Watchman/FLX group, the operator will be able to choose, on the basis of clinical reasons, if to implant Watchman or the new generation Watchman FLX (if available in the center).

In case of impossibility to implant the randomized device, the operator can change the device or stop the procedure

and the patient will be considered for crossover adjudication (see section 8.4).
Fluoroscopy images will be digitalized and encoded for adjudication.

The following evaluations will be performed before, during and after the procedure:

- 12 lead ECG
- TEE or ICE to guide intervention according to the current standard of care
- Procedure-related data collection including duration, fluoroscopic time and overall contrast medium dose as well as any procedure-related complications (described in 5.3)
- Collection of any Serious Adverse Event (SAE) and adverse events of special interest ([AESI] as defined in 11.1 and Appendix 1) up to 48 hours or discharge whichever comes first.

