9.2 Assessments of outcomes

Assessment of primary outcome

The primary outcome is the composite of LAA patency at 45 day evaluated with CCTA or the crossover from one device to the other device based on morphological/anatomical considerations during device implantation.

Patency LAA will be estimated at CCTA by measurement of the linear attenuation coefficient (Hounsfield unit, HU) in the LAA distal to the device and comparison of contrast density to atrial chamber. LAA patency was defined with $HU \geq 100$ or $HU \geq 25\%$ of the atrium, as reported in a previous publication.¹⁵ The occurrence of LAA patency will be centrally evaluated and adjudicated by an Imaging Core Lab (ICL) composed of three imaging experts who will independently score each of the studies as positive or negative for LAA patency. In the event of inconsistent primary end point adjudication between the three readers, a consensus between all of them will be required. Adjunctive CCTA criteria of complete occlusion (as described in section 10.2) will be collected in order to validate them. A TEE evaluation of PDL presence will be performed at 45-days in order to compare the two imaging technique. The crossover is defined as the switch from the randomized device to the other device based on morphological/anatomical considerations during device implantation. It will be centrally adjudicated by CEC as justified if there will be evidence that the randomly allocated device has been positioned at least once in the LAA but LAA ostium sealing remained suboptimal (peri-device leak ≥ 3 mm) or concerns were present over the device stability and consequent risk of device embolization.

Assessment of secondary outcomes

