13. QUALITY ASSURANCE AND CONTROL

13.1 Data handling and record keeping / archiving

The Local Investigator is required to prepare and maintain adequate and accurate case histories designed to record all observations and other data pertinent to the investigation on each individual enrolled in the study.

An electronic data capture (EDC) system will be developed for the study. The software platform selected for this study is ICE-Advice Pharma, a webbased system has an integrated audit trail fulfils the legal requirements for an EDC system. It will include electronic case report forms (eCRFs) designed to capture study information. The forms

will be completed by trained site staff. eCRFs documenting SAEs should be submitted via the EDC system within 24 hours after the investigator becomes aware of the event. All other eCRFs should be completed in a timely manner, preferably within 5-10 days of the subject's enrolment or follow-up visit.

The subject's anonymity will be maintained and the confidentiality of records and documents that could identify subjects will be protected, respecting the privacy and confidentiality rules in accordance with applicable legal requirements. Patients data will be encoded:

- Subjects will be identified only by their assigned study number and year of birth on all CRFs
- The investigator will keep a Patient Identification List with complete identification information (name, address, contact number) on each subject.
- The investigator will maintain all study documents in strict confidence.
- CRF entries will be performed by authorized persons only, who will validate the data with an electronic signature after entering it into the eCRF. Copy of procedural angiogram, cardiac CCTA, TEE and ECG will be stored at the main site in Bern.

All data will be cleared of any sensible personal information, patients will be identified by their assigned study number. For end-point adjudication data will be examined without any form of identification (blinded).

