3.3 Data preparation

LAA patency is derived from the average Linear attenuation coefficient within the LAA distal to the device's lobe (artphase_mean2) ≥ 100 HU OR average Linear attenuation coefficient within the LAA distal to the device's lobe $\geq 25\%$ of the average Linear attenuation coefficient within the LAA (artphase_mean2/artphase_mean1 ≥ 0.25), as recorded inside the follow-up 45 days visit of the Consensus estimate (this is the consensus of the three Core laboratory assessments by three different assessors). LAA patency is a marker of leaks in/out of the LA and therefore a marker of potential thrombus material migration from the LAA to blood circulation system.

Cross-overs are captured in the procedure eCRF and Adjudicated by the clinical event adjudication committee, both successful and failed attempts to cross-over.

CTU Bern	Swiss APERO SAP	Version: 2.0	
	Template: CS_STA_TEM-11	Valid from: 17.08.2021	

The primary endpoint is defined as LA patent or adjudicated cross-overs including failed cross-overs.

Table 1: Derivation of LA patency used in the primary outcome.

Outcome	eCRF sheet	Variable	Variable type	Remarks
LAA patency				
patent = 1	CCTA	fu_reader = 6 = Consensus AND (artphase_mean2 ≥ 100 OR artphase_mean2/artphase_mean1 ≥ 0.25)	Categorical Continuous	Consensus assessment of three assessors LAA HU mean distal from device's lobe in arterial phase = artphase_mean2 LA HU mean in arterial phase = artphase_mean1
not patent = 0				artphase_mean2 not missing and not patent as reverse of the above

Clinical events are also adjudicated and these adjudicated events up to 45 days after the LAAC procedure (or randomization date if no procedure was initiated) will be analysed, excluding events occurring before the LAAC procedure (or randomization date if no procedure was initiated) and excluding events occurring on day 46 and later. Adjudicated events beyond 45 days are used for the longer-term follow-up analyses and censored accordingly (e.g. at 1 year, at 5 years).

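### SAP 2.8 states that the adjudication committee is blinded to the randomised device, but nothing in the plan supports this for crossover, a component of the primary endpoint.

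*Combined protocol and SAP*

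**What the plan says.** - **Blinding.** The trial is open-label (Protocol 6.1). SAP 2.8 lists study personnel, monitors and the statistician receiving the raw data as unblinded, then adds that "also the clinical event adjudication committee adjudicating the events is blinded to the randomized device". It makes no exception for crossover.
- **Who rules on crossover.** Protocol 8.4: "The crossover endpoint will be centrally adjudicated by the Clinical Events Committee (CEC) as justified". SAP 3.3 sends it to the same committee: "Cross-overs are captured in the procedure eCRF and Adjudicated by the clinical event adjudication committee, both successful and failed attempts to cross-over".
- **The definition.** Protocol 9.2: "The crossover is defined as the switch from the randomized device to the other device based on morphological/anatomical considerations during device implantation".
- **The criterion.** Under Protocol 8.4 a crossover is justified if "there will be evidence that the randomly allocated device has been positioned at least once in the LAA" and either sealing stayed suboptimal (leak of at least 3 mm) or there was concern over device stability. Protocol 9.2 repeats this.
- **The material.** Protocol 9.1.2: "Fluoroscopy images will be digitalized and encoded for adjudication". Protocol 13.1 says that data for endpoint adjudication are examined with identification removed, and calls this blinded.
- **Which crossovers are events.** SAP 3.3 counts adjudicated crossovers, including failed ones. SAP 4.2 counts crossover patients as primary events in all analyses and does not mention adjudication.

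**The concern.** A blinded committee is the main safeguard for a judged endpoint in an open-label trial. Here the crossover ruling is partly subjective, because concern over device stability is enough and no threshold is set for it. The trial is supported by a grant from the manufacturer of one of the devices (Protocol 15), so readers will look to the blinding statement for reassurance. If the committee can tell which device was allocated, SAP 2.8 promises more than the design delivers for a primary component, and a report based on it would repeat the claim. How much the result depends on the committee's rulings would also be only partly visible, because no planned analysis counts all recorded crossovers.

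**Working it through.** **1. Does the described process keep the device hidden?**

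| Element | Where | Effect on blinding |
|---|---|---|
| Criterion refers to the randomly allocated device | Protocol 8.4, 9.2 | Does not by itself reveal the arm: a summary could say only allocated device and other device |
| Two arms, and crossover is a switch to the other one | Protocol 9.2 | Recognising either device, and the order of use, identifies the allocation |
| Fluoroscopy images supplied | Protocol 9.1.2 | The device is likely to be visible |
| Plug-and-disc versus plug-only design | Protocol 3.1; SAP 5.9 | The devices can probably be told apart |
| Images encoded, identification removed | Protocol 9.1.2, 13.1 | The 13.1 sentence sits with text on removing personal data; 9.1.2 does not say what is encoded. Neither describes masking the device |
| Other methods of minimising bias | Protocol 6.3 | Marked not applicable |

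That the devices can be distinguished on fluoroscopy is an inference from their described structure. The documents do not state it.

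**2. When does the ruling change a patient's status?** Reading SAP 3.3 as written:

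| 45-day CCTA in a crossover patient | Ruled justified | Ruled not justified |
|---|---|---|
| Patent | Event | Event |
| Not patent | Event | Non-event |
| Not available or not assessable | Event | Missing, excluded under Protocol 12.5 |

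Only the last two rows depend on the committee. If SAP 4.2 is read literally, every crossover patient is an event and the ruling changes nothing. The two sections therefore imply different stakes.

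**3. Scale.** The plan's own figure first. SAP 2.3 gives 200 patients, 50% versus 30%, alpha 5% and power above 80%. With 100 per arm, the two-sided chi-square formula and pooled rate 0.40:

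- s0 = √(2 × 0.40 × 0.60 / 100) = 0.0693
- s1 = √((0.50 × 0.50 + 0.30 × 0.70) / 100) = 0.0678
- power = Φ((0.20 − 1.96 × 0.0693) / 0.0678) = 82.8%, so the stated figure reproduces.

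Now let the rulings shift a net k patients per 100 in the Watchman/FLX arm. The value of k is an assumption. For the false-positive columns, a true rate of 40% in both arms is also assumed and k events are added. For the power column, the planned 50% versus 30% is used and k events are removed. The chance of a false result favouring Amulet is 1 − Φ((1.96 × s0 − k/100) / s1). For k = 2, s0 = 0.0696 and s1 = 0.0695, so the argument is (0.1363 − 0.02) / 0.0695 = 1.67 and the chance is 4.7%.

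| k | False result favouring Amulet | Total two-sided error | Power if k Watchman/FLX events are lost |
|---|---|---|---|
| 0 | 2.5% | 5.0% | 82.8% |
| 1 | 3.5% | 5.2% | 78.9% |
| 2 | 4.7% | 5.9% | 74.6% |
| 3 | 6.3% | 7.1% | 69.8% |
| 5 | 10.6% | 11.0% | 59.2% |

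The table shows sensitivity to a few rulings in either direction. It is not an estimate of bias in this trial.

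**The case against.** The strongest reply is that the plan affirms blinding three times: in SAP 2.8, in the encoding of images (Protocol 9.1.2) and in Protocol 13.1. SAP 5.7 also calls the committee independent and multidisciplinary, and Protocol 2.3 declares independence and disclosure of the funding. What the committee actually receives is not described, and the crossover criterion could be applied to a summary that names no device. All of this stands against several stronger readings.

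- **That crossover is adjudicated unblinded, or cannot be blinded.** A reader might infer this, but no document says it and a masked summary is possible in principle. What holds is that no such step is described and that images are supplied.
- **That SAP 2.8 also misstates the CCTA reading.** It makes no blinding claim for the Imaging Core Lab. SAP 3.3 derives patency from numeric Hounsfield thresholds, and the disc-margin readings belong to adjunctive analyses that Protocol 10.2 places outside the study endpoints.
- **That one or two changed rulings would reverse the result.** This needs a chosen borderline case. At 44 versus 30 events per 100, Fisher's test gives p = 0.057 but the uncorrected chi-square gives 0.040, and SAP 4.1 allows either test. At 47 versus 30, both are below 0.05 (0.020 and 0.013). A crossover patient with a patent appendage is an event in any case.

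Table 4 in SAP 5.7 already reports patency and justified crossover separately, so part of the dependence will be visible. It does not show the composite with all recorded crossovers counted.

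**Conclusion.** The concern holds as a gap between a stated safeguard and the procedure described. For crossover, blinding to the randomised device is unsupported and probably not achieved. This rests on two inferences: that the devices can be recognised on procedural images, and that encoding means de-identification and not masking of the device. The effect on the result is unknown in size and direction, because the documents give neither a crossover rate nor a rate of disputed rulings. It is limited to crossover patients without a patent appendage on CCTA, and it disappears if SAP 4.2 is applied literally. The documents do not show that a bias exists. The statement should be corrected and the dependence on rulings tested before the results are reported as blindly adjudicated.

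**What to change.** 1. In SAP 2.8, restrict the committee's blinding to clinical events, and say that crossover adjudication from procedural images is not assured to be blinded to device.
2. Prespecify a sensitivity analysis of the primary composite that counts all crossovers recorded in the procedure eCRF, successful and failed, whatever the committee ruled. Report it beside the adjudicated version. It removes dependence on the committee, though not on the open-label operator's decision to switch.
3. Reconcile SAP 4.2 with SAP 3.3, so that it is clear whether a crossover ruled not justified is a primary event.

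The cost is one extra analysis of data already captured (SAP 3.3) and a less favourable blinding statement. No new reader or data collection is needed. Withholding images from the committee is not recommended: it would improve masking but leave the ruling on the unblinded operator's own entries for leak and stability, which weakens central adjudication.
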